### Specific Aim 2.

**Hypothesis 2a:** EOT clot volume and/or percent EOT ICH reduction are related to mRS functional outcome regardless of treatment. The null hypothesis is: *EOT clot volume and/or percent EOT ICH reduction trajectories has/have no effect on functional outcome regardless of treatment.*

**Analysis 2a:** This hypothesis investigates the relationship between the magnitude of clot resolution and functional outcome as measured by dichotomized mRS scores (i.e., mRS 0-3 vs. 4-6) at 180 days post-stroke. This is an important component of analysis that has been missing from other surgical trials and will provide for a very stringent test of volume-reduction hypothesis. The goal of this analysis is to test the importance, or lack thereof, for volume-reduction goals in all study patients. This will be best implemented by considering the relationship between clot resolution and functional outcome, as measured by mRS, irrespective of treatment assignment.

The analysis for this aim will proceed in two phases. In the first phase a model for clot resolution over time will be developed. In the second phase, predicted trajectories from phase one will be used to assess the relationship between the magnitude of clot resolution and “good” outcome at 180 days. Generalized Linear Mixed Models (GLMMs) will be

used to estimate patient-specific clot resolution over time. These models will include a random intercept for each patient to represent unobserved factors that are common to ICH volumes for a given patient and a random slope to represent the heterogeneity of clot-resolution trajectories over time across patients as shown in equation 5.

$$\begin{aligned}
 ICH_{ij} &= \beta_{0i} + \beta_{1i}Time_{ij} + \varepsilon_{ij}, & (5) \\
 \beta_{0i} &= \gamma_{00} + u_{0i} \\
 \beta_{1i} &= \gamma_{10} + u_{1i} \\
 \text{where } \varepsilon_{ij} &\sim N(0, \sigma^2) \text{ and } \begin{pmatrix} u_{0i} \\ u_{1i} \end{pmatrix} \sim N \left[ \begin{pmatrix} 0 \\ 0 \end{pmatrix}, \begin{pmatrix} \tau_0^2 & \tau_{01} \\ \tau_{01} & \tau_1^2 \end{pmatrix} \right]
 \end{aligned}$$

Several extensions to the “base model” described above will be considered by changing the assumptions about the random effects and their variance-covariance matrix structure, including models a) without random intercept, b). without random slope, c) with heteroscedastic within person residual errors, d) with grouped covariance structure by study arm, where the variance-covariance matrix of random effects becomes a block-diagonal matrix, where one block represents the variances and covariances of random effects for MIS+rt-PA arm, and the other block – for the medical management arm and e) heteroscedastic residual errors that are different by study arm. The models will be compared using likelihood ratio tests and Akaike Information Criterion (AIC). In addition, since a ‘plateau’ or ‘floor’ effect of clot resolution over time is likely, subsequent models to statistically test for these fixed effects will consider clot resolution in non-linear terms, such as linear/cubic splines and other non-linear functions. From the final model, the empirical Bayes estimates of the random slopes will be computed to be used in the next phase. The second-phase analysis will be based on multivariable logistic regression models that include the estimated clot resolution trajectories over time, the covariates listed in equation (1) above, and the dichotomized mRS at 180 days post-stroke as the outcome.

**Hypothesis 2b:** There is a percent EOT clot reduction and/or EOT clot volume that maximize(s) the probability of a “good” outcome. The null hypothesis is: *There is no relationship between percent EOT clot reduction and/or EOT clot volume (as dichotomized categories) and “good” functional outcome.*

**Analysis 2b:** In this analysis, the clot resolution will be represented as either percent clot resolved at EOT or the EOT clot size. The following cut-points will be investigated as best predictors of “good” outcome at 180 days: 60, 70 and 80% (EOT percent clot resolved), and 10, 15 and 20 mL (EOT clot volume). For each cut point, a dummy variable will be included in the multivariable logistic regression model for “good” outcome adjusted for covariates in equation (1). The models will also assess whether the best cut-points are treatment dependent by including an interaction term between category or percent EOT clot resolution (or the EOT clot volume) and the treatment group.

The models in aims 2a and 2b will be expanded to consider any mediating or modifying factors for the effect of surgical intervention on functional outcome scores. The statistical investigation of mediators that may have an effect on surgery is motivated by the desire to understand whether there is a causal chain whereby surgery affects clot resolution, which in turn affects functional outcome. Although there is no direct test for the existence of such a causal chain, the data can be examined to explore whether they are consistent with such a hypothesis. The methods proposed by Baron and Kenny will be used in these analyses, where a series of three regression models will be created to test for bivariable associations between surgery on functional outcome, surgery on clot resolution, and clot resolution on functional outcome, respectively.

**Analysis of Secondary Outcomes.** Analysis of the secondary outcomes as described above will proceed in three phases: 1) exploratory, 2) cross-sectional evaluations (30 day mortality and safety events, 180 and 365 day post-stroke outcomes, etc.), 3) full longitudinal evaluations (30 to 365 days), and 4) cost-benefit and cost-effectiveness analyses.

Exploratory Phase. The initial phase of the statistical analysis will consist primarily of exploratory methods that include the examination of these data for indications of unusual observations, inconsistencies, or gaps in any pertinent outcomes and related measures; use of visual techniques (e.g., histograms, box-plots, etc.) to determine the distribution and spread of these data; the calculation of summary statistics (e.g. means, medians, variances, etc.) to determine the central tendencies and variability for continuous variables; and the use of contingency tables to assess frequency distributions for categorical variables. Any unusual observations or outliers will be reviewed with the DCC for possible data entry errors, and verified prior to any analyses performed on the data. Exploratory data analyses will be used to summarize these data for the overall patient population and separately by treatment arm (with appropriate blinding restrictions as required), and will primarily occur in conjunction with DSMB evaluations, that is, before the end of the trial and before unblinding of the leadership team.

Cross-Sectional Phase. The second phase begins after the unblinding, and will compare cross-sectional outcomes between the treatment arms using univariate confirmatory analyses (e.g., t-tests, analysis of variance models, logistic regression models, etc.). These group comparisons will be guided by our initial exploratory analyses. Logistic regression will be used to assess 365-day differences in mRS (0-3 vs. 4-6 and 0-2 vs. 3-6). The logistic models will account for design aspects such as potential within-site clustering that might otherwise lead to biased estimates in the standard errors associated with the regression coefficients. Additionally, these models will control for potentially confounding variables, including pre-randomization ICH volume, IVH volume (or presence, depending on the variability in IHV volumes), baseline stroke severity, age, and co-morbidity (diagnosis of Diabetes or history of cardiovascular disease).

When we consider the secondary analysis of the ordinal mRS, we will estimate a proportional odds model of the form:

$$\log\left(\frac{\gamma_k}{1-\gamma_k}\right) = \alpha_k + \beta X + \theta \cdot TRT \quad (6)$$

where  $\alpha_k = \text{Prob}(\text{mRS} < k)$ ,  $k=0,1,\dots,5$ .

The proportional odds model is very similar to the logistic regression model described above, with the difference being that a treatment effect leads to an increase in the likelihood of a patient being in any subsequently lower mRS category. The probabilities,  $\alpha_k$ , are now cumulative probabilities which incorporates all outcomes below any given level. The set of intercepts,  $\alpha_k$   $k=0, 1, \dots, 5$ , define the initial probabilities of these cumulative levels, covariates are again included through  $\beta$  and  $X$ , and the treatment difference  $\theta$  now describes the log-odds of moving from any cumulatively higher (worse) category, into any cumulatively lower (better) category. For instance, here  $\theta$  describes both how the MIS+rt-PA changes the probability of ICH patients away from a potential mRS category of ‘Dead’ (6) to ‘No Symptoms through Severe Disability’ (0-5), as well as how the MIS+rt-PA changes patient probabilities away from ‘Severe Disability or Dead’ (5,6) to ‘No Symptoms through Moderate Disability’ (0-4) and so forth. This model is more efficient than the simple dichotomous approach since it uses the available information across the scale of the measure. To examine the proportional odds assumption, we will additionally examine generalized logistic models that replace  $\beta$  and  $\theta$  with  $\beta_x$  and  $\theta_x$ , allowing non-parallel effects between successive cumulative categories. In the event that the proportional odds assumption is rejected, we will present results from the generalized logistic models.

Survival models will be constructed to examine the mortality, for the MIS+rt-PA and medically-managed groups. Standard Cox proportional hazard models will initially be examined. These models are commonly written as:

$$h_i(t) = \lambda_0(t) \exp(\gamma X + \phi \cdot TRT) \quad (7)$$

where  $\lambda_0(t)$  is a non-parametric baseline hazard function,  $\gamma$  is a vector of regression coefficients related to the  $X$  covariates and  $\phi$  is the parameter for the treatment effect of MIS+rt-PA on the hazard of death (mortality). This model may be extended by including time-dependent covariates and non-proportional hazards as deemed necessary through diagnostic checks. Observed mortality will also be compared with predicted mortality based on clinical presentation, overall and by treatment group. Predicated mortality will be estimated using the most recent Tuhrim model which takes IVH volume and presence of hydrocephalus into account.

Longitudinal Phase. Finally, the third analysis phase will examine the secondary outcomes that are longitudinally collected at baseline and the follow-up time points (e.g. at 30, 90, 180, 270, and 365 days post-stroke). These data will have within-patient correlations from one time point to the next, making it necessary to use appropriate

analytical methods that properly estimate the coefficients and their associated standard errors in the analysis models. Since the overall goal of the trial is to compare subjects receiving the MIS+rt-PA intervention with subjects receiving medical standard of care, a marginal model estimated using a generalized estimating equations (GEE) technique is appropriate. The GEE technique requires specification of the standard ‘mean’ model, as well as specification of a working ‘association’ model. One strength of GEE is that the parameters of main interest in the mean model (i.e. the intervention effect) are consistent regardless of whether the association model is specified correctly. Generalized Linear Mixed Models (GLMMs) may also be used to estimate subject, surgeon, and site-specific effects.

Cost-effectiveness Analysis. Cost-benefit and incremental cost-effectiveness analyses will be performed using data on length of hospital stay, patient disposition (home, long-term ambulatory and nursing care, death), time to return home, and cost of procedures and hospital stay. These analyses will be performed with respect to both 180 and 365-day periods post-stroke. For cost-benefit analyses, the cost of ICU and the rest of the hospital stay, including the cost of MIS+rt-PA will be considered. Cost data will be obtained from the trial (secondary outcomes) and from the literature. For the incremental cost-effectiveness analysis, the distribution of hazard rates of changes in mRS and in-hospital stay will be applied between the treatment arms, considering both short-term (acute care) and long-term care post-stroke. The model will include a one-year time horizon and a secondary analysis of life-time horizon. The analysis will be generated from the health care system perspective for costs combined with the quality-of-life measures for effectiveness (i.e. SIS, EQ-5D, and Personal Health Utility Interview). Various measures of effectiveness will be employed and the robustness of the findings to changes in the source of patient utility/quality of life measures will be reviewed. This will be supplemented by looking at ranges for patient utilities reported in the literature. Finally, probabilistic sensitivity analyses will be conducted using a bootstrap approach, producing a scatter plot of incremental costs and effects to assess the impact of statistical uncertainty on the robustness of the conclusions.

**9.1.8. Safety Analyses.** The primary safety measures for this study are symptomatic intracranial bleeding, infection, and 30-day mortality. The safety thresholds for these measures have been set as: 30-day mortality > 60%, first week operative death rate > 10%, a MIS and rt-PA related symptomatic brain bleeding rate > 25% (events identified within the first 30 days and assessed as occurring during active treatment or during the 72 hours after treatment will be monitored), and a procedure-related brain infection rate > 15% (over the initial 30 days).

**9.1.8.1. Adverse Events (AE) and Serious Adverse Events (SAE).** All AEs and SAEs are summarized by type and by treatment group in terms of frequency of the event, number of subjects having the event, timing relative to randomization, severity (mild, moderate, severe), and relatedness to the study treatment (definitely, probably, possibly, definitely not). At the end of the study, the cumulative incidences of these events will be compared between the two

treatment groups using Fisher's exact test. Additionally, generalized linear mixed models for binary data will be used to examine AE and SAE probabilities between treatment groups while accounting for potential confounders and sites center clustering effects.

**9.1.8.2. Time to Death and Time to Re-Bleed.** As a secondary assessment, time to death or re-bleed within the one-year follow up period are compared between the MIS+rt-PA and medically-managed groups adjusting for appropriate baseline covariates. Provided the model assumptions are met, a proportional hazards regression model may be used for the analysis as described above.

**9.1.8.3. Safety Monitoring.** The DCC will generate periodic DSMB reports (We assume that the total number of subjects enrolled per six months in a single treatment group will be approximately 30; thus, eight semi-annual looks at the data will be suggested to the DSMB. As usual though, periods for reporting will be discussed and finalized at the initial DSMB meeting). Each report will provide cumulative summary statistics on enrollment; subject status in the study (e.g., number completed at 3-month, 6-month, 9-month, and 12-month assessments); baseline characteristics; protocol violations; safety data, including AEs and SAEs by AE code, severity, and relatedness to the study medication; outcomes data (if coinciding with an interim analysis – also to be discussed and finalized at the initial DSMB meeting); and data management/quality information (e.g., timeliness and completeness of data entry by the clinical sites centers via the MISTIE III Trial Website; number of queries generated and resolved). Closed reports will be generated for the DSMB voting committee members with data provided by blinded treatment group (noted as A and B). Only the unblinded statistician has access to the efficacy endpoint data. These data will not be included in the reports for the safety reviews. The outline of these proposed DSMB reports will be included in the Manual of Operations and Procedures prepared by the Clinical Coordinating Center (CCC). In an interval as yet to be determined (monthly or quarterly), the CCC will also generate a Safety Monitoring Report to be distributed to the DSMB. This report contains only the enrollment, subject study status, safety, and data quality information. The Executive Committee also receives the Safety Monitoring Reports. The DSMB will have discretion to recommend stopping the trial early if safety concerns become substantial. Safety stopping rules for each of the primary safety outcomes will be developed and used to help the DSMB make its safety assessments. The DSMB makes recommendations to NINDS who has authority to stop the investigation for safety or any other reason after discussion with the trial PI.

**9.1.9. Statistical Power for the Primary Efficacy Aim.** The MISTIE Phase II results, for all available data (trial-standardized “pilot” and randomized), demonstrated a best estimate for the increase in the probability of achieving an mRS 0-3 of 13.0% [95% CI: (0.4%, 26.4%)] comparing MIS+rt-PA treatment versus medical

management 180 days post-stroke. When only randomized patients are considered (N=90), the best estimate for the unadjusted effect size is approximately 11.0% [95% CI: (-7.9%, 29.7%)], and approximately 12.0% [95% CI: (-2.7%, 26.9%)] after adjusting for baseline clinical characteristics. These estimated effect sizes are statistically equivalent given the similarity in the CIs. Nevertheless, their range provides a strong motivation for conducting the proposed Phase III trial to confirm these clinically beneficial findings. The analogous unadjusted and adjusted effect sizes based on non-lobar ICH patients are very similar and statistically equivalent to these effect sizes.

In the proposed design, subjects will be randomized to MIS+rt-PA versus medical management using a covariate-adaptive design. The goal of this randomization scheme is to obtain an improved balance across study arms in the number of subjects with certain pre-randomization variables that are strongly predictive of the functional outcomes at 180 days post-stroke. These variables include pre-randomization clot size and baseline severity of impairment as measured by GCS. The design of Pocock and Simon will be used, which increases a newly enrolled subject's probability of being assigned to the study arm that improves the overall balance in these important prognostic factors. The trial will initially enroll ICH patients until either a maximum of 500 patients is accrued or the trial is stopped early for efficacy or futility using group sequential boundaries described below (Table 1).

**Table 1. Efficacy and Futility Boundaries for the Study Population with a Risk-Difference Assuming the Conservative Effect Size of 11%**

Boundary	After 250 patients	After 375 patients	After 500 patients
Efficacy	2.87	2.34	2.03
Futility	-2.30	-1.98	

The above stopping boundaries are used after 250, 375 and 500 patients, respectively, have 180-day post-stroke measurements. If the test statistic described above exceeds the efficacy boundary, or if it is less than the futility boundary, the enrollment of patients is stopped early. The futility boundary at each interim analysis corresponds to a one-sided test at level 0.0001 of the hypothesis that the probability of a “good” outcome (mRS 0-3) is  $\geq 11\%$  under assignment to MIS+rt-PA vs medical management. These boundaries are more aggressive than the efficacy boundaries (the latter of which are based on O'Brien-Fleming boundaries, but are proportionally increased to strongly control the study-wide Type I error rate at the 5% level).

The above design has the following properties as described in Figure 1 and Table 2:

- i) At least 88% power to detect a treatment benefit  $\geq 13\%$ , assuming the probability of mRS 0-3 under medical management is 25%;

- ii) At least 81% power to detect a treatment benefit  $\geq 11\%$ , assuming the probability of mRS 0-3 under medical management is 20%.

**Table 2. Estimated Power for Risk-Difference Effect Sizesa from 10-13% (N=500) by Probability of mRS 0-3 in Medical Management Arm**

	Base Plan b	Plan B b
Effect Size	Probability = 0.25	Probability = 0.20
13%	88%	91%
12%	83%	87%
11%	76%	81%
10%	68%	73%

a MIS+rt-PA – medical management

b Tables 4, 5 in CCC grant

[figure not shown]

Figure 1. Power curves at ranges of effect sizes on risk difference scale, assuming baseline probability of modified Rankin Score 0-3 for medically-managed patients = 25%

**9.1.10. Statistical Power for Secondary Aim 2a.** Based on MISTIE II data (Table 1), the relationship between mRS score and EOT clot size is estimated as an OR (95% CI) of 3.82 (0.97-15.1,  $p=0.056$ ). Simulations were performed on 1000 generated samples of 250 patients per group based on randomized MISTIE II patient data. These simulations indicate that with 500 total patients the estimated power to detect an adjusted OR of 3.82 is  $\geq 98\%$ . Additional simulations suggest that there is  $\geq 90\%$  power for detecting an adjusted OR as low as 2.38 to evaluate the strength of the relationship between clot size, dichotomized as  $\leq 15$  vs  $> 15$  mL and mRS outcome (0-3 vs 4-6).

**9.1.11. Innovative Methods.** Categorical outcomes such as the mRS, GOS, etc, are termed composite outcomes in the statistical literature as they combine outcomes of interest such as ability/disability with mortality outcomes. There have been recent methods developed to allow simultaneous examination of the ability/disability and mortality outcomes but they do not specifically include

mortality in the actual outcome scale. Joint analyses based on generalized linear mixed models (GLMM) have been introduced, and are proposed to extend these models for the brain injury/stroke literature using data from this trial. A latent Gaussian process will be posited to represent an individual's underlying propensity to regain ability which describes relationships between a subject's longitudinal outcomes. A random effects model corresponding to the dichotomous mRS logistic regression model outlined above may be specified as:

$$\begin{aligned} (\text{logit}(\text{Prob}[Y_{ij} \leq 3])) &= \beta_0 + \beta_{0i} + \theta T_{rt} + \beta X_{ij} \\ \beta_{0i} &\sim N(0, \tau^2) \end{aligned} \quad (8)$$

where  $Y$  is the binary outcome for patient  $i$  at the time  $j$  and  $Y_{ij}=1$  if  $\text{mRS}_{ij}=0-2$  and  $Y_{ij}=0$  if  $\text{mRS}_{ij}=3-5$ . Note that the category  $\text{mRS}_{ij}=6$ , indicating death, has been removed from the outcome definition such that  $Y_{ij}$  describes ability for those remaining alive at time  $j$ .

**9.1.12. Missing Data.** Based on previous MISTIE and CLEAR studies performed in this group of stroke patients, the CCC will make substantial efforts to ensure complete collection of data for all patients, and to accrue minimal LTF to optimize evaluation of the primary outcome of 180-day adjudicated mRS post-stroke. In the CLEAR III trial, there is a LTF of 2% among the first 100 patients as reported to the DSMB. Rates of missing data and LTF will be reported, and no imputation of the primary outcome measure will be undertaken. However, multiple imputation methods based on regression modeling will be used to estimate missing covariates incorporated in the logistic regression model for estimating the adjusted treatment effect. In addition, the effects of incompleteness/noncompliance will be quantified through sensitivity analyses, the gold standard in the field.

**9.1.13. Multiplicity.** The study design for the primary comparison is a two-arm randomized trial with a single-treatment contrast, hence, multiplicity from several tests is not an issue.

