**Safety Monitoring and Recruitment Suspension Rules.** Safety events above pre-specified thresholds will trigger “a suspend recruitment and review “by the DSMB to investigate the presumed cause and impact of these events. Such events are initially reviewed by a Data Coordinating Center (DCC) staff member to determine if an event threshold has been reached at which time the study investigators and the DSMB will be notified. The thresholds triggering such a review are: 30-day mortality > 60%, a MIS+rt-PA related symptomatic bleeding rate > 25% (events identified within the first 30 days and assessed as occurring during active treatment or during the 72 hours after treatment will be monitored), first week operative death rate > 10%, and a procedure-related infection rate > 15% (over the initial 30 days). If any of these SAEs are attributable to the intervention (catheter insertion or manipulation, or rt-PA injection), the study will be suspended for a complete safety and efficacy review.

**Efficacy Monitoring and Recruitment Suspension Rules.** Interim analyses for safety will occur after 125, 250, 375 and 500 subjects are enrolled. One interim look at efficacy and futility will occur after 375 subjects are enrolled. These analyses will be based on ‘Brien-Fleming’ stopping boundaries for efficacy and more aggressive (i.e., more likely to stop if there is no early signal of benefit) stopping boundaries for futility.(Jennison C, Group sequential methods with applications to clinical trials. Boca Raton, FL. Chapman & Hall/CRC Press, 2000.)

**9.1.1. Randomization.** Subjects will be randomized to MIS+rt-PA surgery: medical management using a covariate-adaptive design similar to that used for the CLEAR III trial. The goal of this randomization scheme is to obtain an improved balance across study arms in the number of subjects with certain pre-randomization variables that are strongly predictive of the functional outcomes

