**9.1.7. Efficacy Analyses**

**9.1.7.a.** Analysis by MISTIE III Specific Aims

Primary Aims

**Hypothesis 1a:** Minimally invasive surgery (MIS) plus recombinant tissue plasminogen activator (rt-PA) for 3 days for the treatment of ICH improves functional outcome at 180 days as measured by the adjudicated mRS 0-3 by an estimated 13% increase as compared to the medically-managed patients. The null hypothesis will be a test of no improvement of MIS+rt-PA over medical management. Below is a description of the procedure for computing estimators of the treatment difference in probability of mRS 0-3 at 180 days post-stroke, for the study's population.

**Analysis 1a:** To evaluate this null hypothesis in the context of the covariate-adaptive randomization scheme, the model in equation (1) will be used, where Trt is 1 for MIS+rt-PA patients and 0 for medically-managed patients, ICH is pre-randomization ICH clot volume, GCS, Age, Diabetes and CVD (cardiovascular disease) are at randomization.

$$(\text{logit}(\text{Prob}[mRS \leq 3])) = \beta_0 + \beta_1 \text{Trt} + \beta_2 \text{ICH} + \beta_3 \text{GCS} + \beta_4 \text{Age} + \beta_5 \text{Diabetes} + \beta_6 \text{CVD} \quad (1)$$

The standardized estimator of the marginal treatment effect, in the form of RD, will then be computed. The advantage of this estimator, compared to the estimator based on a simple test of proportions using a z-test without covariates, is that it can lead to greater power for hypothesis testing.

The estimator in this approach is standardized to the overall distribution of covariates in equation (1) across the two treatment arms. Under this framework, the probability of a good outcome is defined under two scenarios for each patient: if assigned to MIS+rt-PA treatment vs. if assigned to the standard medical treatment arm (i.e. the counter-factual probabilities). The counter-factual probabilities based on model 1 are presented below as equations (2) and (3):

$$\mu_{1i} = \text{logit}^{-1}(\hat{\beta}_0 + \hat{\beta}_1 + \hat{\beta}_2 ICH_i + \hat{\beta}_3 GCS_i + \hat{\beta}_4 Age_i + \hat{\beta}_5 Diabetes_i + \hat{\beta}_6 CVD_i) \quad (2)$$

$$\mu_{0i} = \text{logit}^{-1}(\hat{\beta}_0 + \hat{\beta}_2 ICH_i + \hat{\beta}_3 GCS_i + \hat{\beta}_4 Age_i + \hat{\beta}_5 Diabetes_i + \hat{\beta}_6 CVD_i) \quad (3)$$

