12.0. Interim Efficacy Analyses

At the discretion of the DSMB, a formal interim efficacy analysis will occur after 375 subjects reach 180 days of follow-up. These analyses will be based on approximate O'Brien-Fleming stopping boundaries for efficacy (defined below).

In the MISTIE III design, subjects will be randomized to MIS+rt-PA versus medical management using a covariate-adaptive design described previously. The trial will initially enroll ICH patients until either a maximum of 500 eligible patients is accrued or the trial is stopped early for efficacy or futility using group sequential boundaries described below.

Analyses will be conducted after 375 and 500 patients, respectively, have 180-day post-stroke measurements. Efficacy stopping boundaries will be based on the error-spending (also called alpha-spending) approach using the power family with exponent rho=3, which approximates the O'Brien-Fleming boundaries. The (one-sided) alpha allocated to the analysis (called the interim analysis) at 375 participants is defined to be alpha₁ = $0.025(375/500)^3 = 0.0105$. All remaining alpha, i.e., (0.025-alpha₁) is spent at the analysis with 500 participants (called the final analysis).

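### Protocol Table 1's futility boundary of -1.98 at 375 patients does not follow from its stated level and effect, which give about -1.26 to -1.39, and SAP 12.0 gives no futility value

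*Protocol*

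**What the plan says.** Protocol 9.1.9, Table 1, is titled "Efficacy and Futility Boundaries for the Study Population with a Risk-Difference Assuming the Conservative Effect Size of 11"%. Its futility row reads -2.30 after 250 patients and -1.98 after 375. Its efficacy row reads 2.87, 2.34 and 2.03.

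The text under the table makes these values operative: "The above stopping boundaries are used after 250, 375 and 500 patients, respectively, have 180-day post-stroke measurements". On futility it says that "if it is less than the futility boundary, the enrollment of patients is stopped early". It then defines the row: "The futility boundary at each interim analysis corresponds to a one-sided test at level 0.0001 of the hypothesis" of an 11% benefit. The control rates used in the same section are 25% (base plan) and 20% (the rate paired with the 11-point effect).

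Protocol 9.1, Efficacy Monitoring and Recruitment Suspension Rules, keeps a single look: "One interim look at efficacy and futility will occur after 375 subjects are enrolled".

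SAP 12.0 agrees on one look: "At the discretion of the DSMB, a formal interim efficacy analysis will occur after 375 subjects reach 180 days of follow-up". It says that enrolment runs to 500 patients unless "the trial is stopped early for efficacy or futility using group sequential boundaries described below". What follows is an efficacy spending rule only; no futility boundary or rule is given.

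**The concern.** A one-sided test at a stated level, of a stated risk difference, at a stated number of patients fixes the boundary on the Z scale once an event rate is chosen. The printed futility values should therefore be recoverable from the plan's own inputs, as the efficacy row is. If they are not, the DSMB holds a number and a definition that disagree, and they give materially different chances of stopping when surgery shows no benefit or does harm. The SAP does not settle which one governs.

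**Working it through.** **Inputs**
- One-sided level 0.0001, so z = 3.719 (Protocol 9.1.9).
- Risk difference 0.11 (Table 1 title).
- Control rate 20% or 25% (Protocol 9.1.9), hence surgical rate 31% or 36%.
- 1:1 allocation: 125 per arm at 250 patients, 187.5 per arm at 375.
- Test statistic: Wald ratio of the risk difference to its standard error (Protocol 9.1.7.a, Analysis 1a).

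**Efficacy row first.** An O'Brien-Fleming shape is 2.03 × √(500/n):
- n = 250: 2.03 × 1.414 = 2.87
- n = 375: 2.03 × 1.155 = 2.34
- n = 500: 2.03

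All three printed values reproduce. The eight powers in Table 2 also reproduce within one point.

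**Futility row.** Rejecting a benefit of at least 0.11 at level 0.0001 means (RD − 0.11)/SE < −3.719. On the scale Z = RD/SE, the boundary is 0.11/SE − 3.719, with SE = √{[p0(1−p0) + p1(1−p1)]/n per arm}.

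| Patients | Rates | SE | 0.11/SE | Boundary | Printed |
|---|---|---|---|---|---|
| 250 | 20% vs 31% | 0.05469 | 2.011 | -1.71 | -2.30 |
| 250 | 25% vs 36% | 0.05782 | 1.902 | -1.82 | -2.30 |
| 375 | 20% vs 31% | 0.04466 | 2.463 | -1.26 | -1.98 |
| 375 | 25% vs 36% | 0.04721 | 2.330 | -1.39 | -1.98 |

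**Other readings at 375 (20% / 25% control)**
- Pooled SE: -1.28 / -1.41
- Log-odds scale: -1.29 / -1.42
- Continuity correction: -1.38 / -1.50
- Two-sided 0.0001 (z = 3.891): -1.43 / -1.56
- Largest possible binomial variance (both rates 50%, SE 0.0516): -1.59

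Reaching -1.98 needs p0(1−p0) + p1(1−p1) = 187.5 × [0.11/(3.719 − 1.98)]² = 0.75. Two proportions cannot exceed 0.50. Covariate adjustment does not help: the protocol adopts it because "it can lead to greater power for hypothesis testing", which means a smaller SE and a boundary further from -1.98.

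**Where the printed values may come from.** With 20% vs 31% and half the stated patients (62.5 and 93.75 per arm), the same formula gives -2.297 and -1.977, matching both entries to two decimals. This points to a factor-of-two slip in the sample size and supports the risk-difference reading. It is an inference, because the documents do not show the derivation.

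**What -1.98 means at 375.** The implied level is Φ(−1.98 − 0.11/SE):
- 20% control: 0.0000044, about 23 times stricter than 0.0001
- 25% control: 0.0000082, about 12 times stricter
- Largest variance: 0.0000198, about 5 times stricter

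The observed difference d at which Z reaches each boundary, solving d/SE(d) = boundary, and the chance of a futility stop at that look (normal approximation) are:

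| | Printed, 20% | Definition, 20% | Printed, 25% | Definition, 25% |
|---|---|---|---|---|
| Observed difference, points | -7.5 | -4.9 | -8.3 | -5.9 |
| Stop, no effect | 2.4% | 10.5% | 2.4% | 8.2% |
| Stop, true 5-point harm (illustrative assumption) | 24% | 51% | 21% | 41% |
| Stop, true 11-point benefit | 0.0004% | 0.01% | 0.0008% | 0.01% |

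**SAP.** The only boundary defined is for efficacy: 0.025 × 0.75³ = 0.0105 one-sided at 375, or Z = 2.31 in place of Table 1's 2.34.

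**The case against.** The arithmetic is not disputed. The objections concern the replacement value, the remedy and the weight.

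- **Loose source.** The defining sentence is badly worded and its cited method is not in the documents. This is a fair caution. But the table title says risk difference, and the half-sample match recovers both printed values under exactly this formula.
- **Replacement not unique.** -1.26 and -1.39 use the SE at the design alternative. The Wald statistic divides by its estimated SE. Solving (d − 0.11)/SE(d) = −3.719 at 375 gives d = -3.8 points and Z about -0.95 (20%), or d = -5.0 points and Z about -1.16 (25%). This stands as a reason to state the convention, but it widens the gap from -1.98.
- **Keeping -1.98 may legitimise a slip.** No single level fits both printed values: at 20% control, -2.30 implies 0.0000081 and -1.98 implies 0.0000044. This is true of the row as printed. With one retained look at 375, a single restated level is coherent.
- **Small practical effect.** The rule bites only when surgery looks several points worse, where separate safety thresholds and DSMB discretion apply. At the planned 30 patients per arm per six months, about 375 + 60 = 435 would be enrolled when 375 reach 180 days, so a stop spares about 65. In the 5-point-harm scenario, the 20 to 27 point difference in stopping probability is about 13 to 17 patients in expectation; with no effect, about 4 to 5. This stands and limits the weight of the point.
- **Whether the DSMB would use -1.98 is uncertain.** SAP 12.0 leaves the formal interim to its discretion. But the protocol makes the printed values operative and no other futility number exists.

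**Conclusion.** The concern holds. Table 1's futility row contradicts the level and effect stated for it, and no pair of event rates at the stated patient numbers reconciles them. Either the threshold or its stated level or effect is wrong. The size depends on the protocol's control rates of 20% to 25%, unadjusted binomial variance at the design alternative, and 1:1 allocation.

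The consequence is bounded. The printed boundary makes a futility stop less likely than its definition implies, and a true 11-point benefit is almost never stopped under either rule. The primary conclusion is not threatened. It should still be fixed, because it is a decision threshold that the protocol puts into use and the SAP neither restates nor corrects.

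**What to change.** 1. In Protocol 9.1.9, choose one:
   - recompute the futility value at the actual patient numbers, stating the control rate and SE convention (at 375, with the SE at the design alternative, -1.26 for 20% or -1.39 for 25%); or
   - keep -1.98 and restate what it corresponds to (for an 11-point benefit, level 0.0000044 at 20% control or 0.0000082 at 25%).

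   If the derivation shows that the sample size was halved by mistake, the first option is the right one.
2. Reword the defining sentence so that it plainly refers to a risk difference of at least 11 points.
3. Put the single 375-patient futility value in SAP 12.0 and say whether it is binding. If futility stopping is no longer intended, say so.
4. Reconcile Table 1's 250-patient column with the single look in Protocol 9.1 and SAP 12.0.

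The cost is protocol and SAP wording. Sample size, efficacy boundaries and power do not change.
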